Trough concentrations on Cycle 1 Day 8, day 15 and Cycle 2 day 1 (pre-dose and 24 hour) will be displayed graphically. Scatter plots of PK parameters versus dose, or log-dose will also be considered following both single and multiple dose administration of AZD9291 to visually inspect dose proportionality.

Safety data will not be formally analysed. All patients who receive at least one dose of AZD9291 will be included in the assessment of the safety profile. At the end of the study, appropriate summaries of all safety data will be produced.

Tumour response data will be listed and summarised by dose group, and if appropriate using the following response categories: Complete Response (CR), Partial Response (PR), Stable Disease (SD), Progressive Disease (PD) and Non-Evaluable (NE). The data cut-off for preliminary efficacy analysis will take place approximately 3 months after the last subject has been enrolled, to allow opportunity for all patients to complete a minimum of two RECIST follow-up assessments.

TABLE OF CONTENTS

PAGE

3
8
17
17
17
20
20
20
20 21 24 25 26 26 26
20 21 24 25 26 26 26 27
20
20 21 24 25 26 26 26 26 27 28 29
20
20 21 24 25 26 26 26 26 26 27 28 29 29 29 30
20 21 24 25 26 26 26 26 26 27 28 29 29 29 30 30
20 21 24 25 26 26 26 26 26 27 28 29 29 29 30 30 30 30
20 21 24 25 26 26 26 27 28 29 29 29 30 30 30 31

5 1 2	Overall henefit_risk and ethical assessment	31
5.5 5.5.1	Discontinuation of investigational product and withdrawal from study Procedures for discontinuation of a patient from investigational product	32
5.5.2	Procedures for handling patients incorrectly initiated on investigational	22
553	Procedures for withdrawal from study	
5.6	Study timetable and	33
5.0		
6.	STUDY PLAN AND COLLECTION OF STUDY VARIABLES	33
6.1	Study Plan	33
6.2	Recording of data	36
6.3	Safety procedures	36
6.3.1	Enrollment and screening	36
6.3.2	Physical examination	37
6.3.3	Vital signs	37
6.3.3.1	Pulse and blood pressure	37
6.3.3.2	Weight and height	57
0.3.4	EUG	
636	Constant of a second se	
637	Fchocardiogram/MUGA Scan	40
638	Follow-up	40
6.3.8.1	Discontinuation Visit	
6.3.8.2	Safety Follow-Up	40
6.4	Adverse events	
6.4.1	Definition of adverse events	
6.4.2	Definitions of serious adverse events	41
6.4.3	Recording of adverse events	41
6.4.4	Reporting of serious adverse events	45
6.5	Pharmacokinetics	
6.5.1	Collection of pharmacokinetic samples	
6.5.2	Determination of drug concentration in pharmacokinetic samples	47
66	Biological sampling procedures	47

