1. STUDY OBJECTIVE

1.1 Primary objective

To characterise the pharmacokinetics (PK) of AZD9291 and its metabolites (AZ5104 and AZ7550) after single then multiple doses of AZD9291 administered orally once daily in Chinese patients with locally advanced or metastatic non-small cell lung Cancer (NSCLC) who have progressed following prior therapy with an approved Epidermal Growth Factor Receptor (EGFR) Tyrosine Kinase Inhibitor (TKI) agent.

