3.1 Overall study design and flow chart

This is a phase I, open-label, two parts (Part A and Part B) study to determine the pharmacokinetics of AZD9291 administered orally at two dose levels (40 mg and 80 mg) in patients with locally advanced or metastatic NSCLC who have progressed following prior therapy with an approved EGFR TKI agent (+/- additional chemotherapy regimens).

Approximately 24 patients will enter into this study, with 12 patients at each dose level

- Cohort 1 will investigate the pharmacokinetics of single then multiple dosing of AZD9291 at 40 mg once daily dose.
- Cohort 2 will investigate the pharmacokinetics of single then multiple dosing of AZD9291 at 80 mg once daily dose.

The enrollment of Cohort 2 will start after Cohort 1 finishes the enrollment. The first 12 patients enrolled in the study will be in 40 mg dose Cohort.

Patients will be administered a single dose of AZD9291 on Day 1, Cycle 0 at the beginning of Part A period. From Day 2 to Day 6, no treatment will be given, but PK samples will be obtained; on Day 8 (Cycle1, Day1), the patients will be administered AZD9291 once daily on a continuous schedule, ie, no break in AZD9291 dosing. Part A will complete after Cycle 4 treatment and Part B will start without treatment interruption.

Patients in both cohorts should continue on treatment with AZD9291 until a treatment discontinuation criterion is met. There is no maximum duration of treatment as patients may continue to receive AZD9291 beyond RECIST 1.1 defined progression as long as they are continuing to receive clinical benefit, as judged by the investigator.

The whole study will be divided nominally into two parts: Part A will assess the pharmacokinetics and preliminary efficacy and safety of AZD9291 at 40 mg and 80 mg respectively, and Part B will assess only the safety and efficacy data of AZD9291.

Following completion of the Part A, patients will automatically continue to Part B.

There are two data cut offs:

- 1. PK and preliminary efficacy and safety data base lock will take place approximately 3 months after LSI and after the part A completes, to allow all patients have two tumor assessments after the first dose.

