7.2 Determination of sample size

The primary objective of this study is to characterise the pharmacokinetics (PK) of AZD9291 after a single then multiple oral doses of AZD929. The key secondary objective is to investigate the safety and tolerability of AZD9291 to recommend dose(s) for evaluation in future clinical studies. Hence the number of patients in the cohorts has been based on the desire to obtain adequate tolerability, safety and pharmacokinetic data while exposing as few patients as possible to the investigational product and procedures. Tumour response as measured using RECIST 1.1 will be assessed to provide preliminary anti-tumour activity in targeted patient population.

Approximately 12 patients with advanced NSCLC will be enrolled in each cohort

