The following summary statistics will be presented for AUC, $AUC_{(0-24)}$, $AUC_{(0-t)}$, AUC_{ss} , C_{max} , $C_{ss max}$, $C_{ss min}$, CL/F, CL_{ss}/F , volume of distribution, $t_{\nu_{2}\lambda_{Z}}$, R_{AC} , time dependency, lambda_z, R-square, % AUC extrapolated, MRC_{max} and MRAUC:

- Gmean, calculated as $exp[\mu]$, where μ is the mean of the data on a logarithmic scale)
- CV, calculated as $100 \sqrt{[\exp(s_2)-1]}$, where s is the standard deviation of the data on a log scale)
- Arithmetic mean calculated using untransformed data
- Standard deviation calculated using untransformed data

- Minimum
- Maximum
- Number of observations

The following summary statistics will be presented for t_{max} and t_{max ss}:

- Median
- Minimum
- Maximum
- Number of observations

The following summary statistics will be presented for MRT:

- Arithmetic mean
- Standard deviation
- Median
- Minimum
- Maximum
- Number of observations

The pharmacokinetic data for AZD9291, AZ5104 and AZ7550 after a single-dose and separately, at steady state will also be displayed graphically. Displays will include plasma concentration patient profiles (on the linear and log-scale) versus time and gmean concentration (+/-standard deviation) versus time, stratified by dose.

Scatter plots of PK parameters versus dose, or log-dose will also be considered following both single and multiple dose administration of AZD9291 to visually inspect dose proportionality.

Tumour response

The analysis population for objective tumour response will be the "evaluable for response" population.

Tumour response data will be listed and if appropriate using the following response categories: Complete Response (CR), Partial Response (PR), Stable Disease (SD), Progressive Disease (PD) and Non-Evaluable (NE).

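### The only method the protocol names for dose proportionality is optional scatter plots read by eye; a dose-normalised 80/40 mg ratio with a 90% CI would show how little 12 per cohort can exclude

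*Protocol*

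**What the plan says.** On dose proportionality, protocol section 7.7 (Pharmacokinetics) says: "Scatter plots of PK parameters versus dose, or log-dose will also be considered following both single and multiple dose administration of AZD9291", the purpose being "to visually inspect dose proportionality". The synopsis, under Statistical methods, says the same ("Scatter plots of PK parameters versus dose, or log-dose will also be considered"). No ratio, power model, interval or criterion appears in either place.

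Section 7.7 also commits to summaries by dose level. For AUC, AUC(0-24), AUCss, Cmax, Css,max, CL/F and CLss/F it lists the geometric mean, geometric CV, arithmetic mean, SD, range and number of observations. Section 7.4 defines CL/F and CLss/F as dose over AUC and dose over AUCss, and restricts both to AZD9291.

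On the design, section 3.1 states: "Approximately 24 patients will enter into this study, with 12 patients at each dose level", and "The enrollment of Cohort 2 will start after Cohort 1 finishes the enrollment". Section 7.2 gives no precision target; "the number of patients in the cohorts has been based on the desire to obtain adequate tolerability, safety and pharmacokinetic data". The primary objective in section 1.1 is "To characterise the pharmacokinetics (PK) of AZD9291 and its metabolites (AZ5104 and AZ7550) after single then multiple doses of AZD9291 administered orally once daily". Proportionality is not mentioned there, in section 1.2, or among the endpoints in section 7.1.

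**The concern.** There are two dose levels with different patients at each, so a plot of a PK parameter against dose is two columns of points. Shape across doses cannot be judged from two columns. The one quantity they can inform is the ratio of exposure at 80 mg to exposure at 40 mg after allowing for dose. A plot gives neither that ratio nor its uncertainty, and the eye is poor at separating a real departure from between-patient spread.

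The synopsis frames the primary objective around the two dose levels, so how exposure changes between them is of natural interest. If the report says only that the plots looked proportional, a reader may take more from it than the data can bear.

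**Working it through.** **Nothing to reproduce.** The 12 per cohort rests on no stated calculation, so there is no planned figure to check first.

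**Inputs.**
- Patients: 12 per cohort (section 7.2, "Approximately 12 patients with advanced NSCLC will be enrolled in each cohort").
- Doses: 40 and 80 mg, a ratio of 2 (section 3.1).
- Between-patient CV: not given in the protocol. Assumed to be 30% to 60%, equal in the two cohorts.

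**Formulas.** Let R be the ratio of geometric means of exposure divided by dose, 80 mg over 40 mg; R = 1 is exact proportionality.
- Log-scale SD: s = sqrt(ln(1 + CV²)), the inverse of the CV formula in section 7.7.
- Standard error of ln R: s × sqrt(2/12) = 0.408 s.
- 90% half-width: h = t(0.95; 22 df) × SE = 1.717 × 0.408 s.
- The interval is the estimate of R times or divided by exp(h). With two doses, the power-model slope has half-width h / ln 2.

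**One case in full, CV 40%.** s = sqrt(ln 1.16) = 0.385. h = 1.717 × 0.408 × 0.385 = 0.270. exp(0.270) = 1.31. Slope half-width = 0.270 / 0.693 = 0.39.

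**All cases, 12 per cohort, observed ratio 1.00.**

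| Assumed CV | s | Factor exp(h) | 90% CI | Slope half-width |
|---|---|---|---|---|
| 30% | 0.294 | 1.23 | 0.81 to 1.23 | 0.30 |
| 40% | 0.385 | 1.31 | 0.76 to 1.31 | 0.39 |
| 50% | 0.472 | 1.39 | 0.72 to 1.39 | 0.48 |
| 60% | 0.555 | 1.48 | 0.68 to 1.48 | 0.56 |

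**Fewer evaluable patients.** Section 7.6 removes patients with important deviations or adverse events that may affect PK, and section 7.4 extrapolates AUC to infinity only where appropriate. With 10 per cohort (18 df) the intervals are 0.80 to 1.26 at CV 30%, 0.74 to 1.35 at 40%, 0.69 to 1.44 at 50% and 0.65 to 1.54 at 60%.

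**What 12 per cohort can support.** Simulating exact proportionality (200,000 runs), the 90% CI falls wholly within 0.80 to 1.25 about 16% of the time at CV 30%, 1% at 40% and practically never from 50% up. These limits are a yardstick only; the protocol sets none.

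**What the planned tables already give.** Since CL/F is dose/AUC, the 80/40 ratio of geometric mean CL/F is 1/R for AUC; CLss/F does the same for AUCss. That covers two parameters for AZD9291. For Cmax, Css,max, AUC(0-24) and both metabolites, the reader would have to divide by dose, and for every parameter would have to build the interval from the CVs and numbers. All the ingredients are in tables already planned.

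**The case against.** The strongest reply is that this is descriptive PK in 24 patients, handled descriptively. Plots are described as an optional addition, so nothing excludes a ratio or power model, and the statistical analysis plan, which is not at hand, may name one. Numerical summaries by dose are fixed, and clearance gives the parent's dose-normalised AUC comparison outright. No criterion, verdict or decision is tied to proportionality. Section 7.4.1 also foresees possible pooling with other studies in population PK work.

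Most of this stands, and it limits the point. A reader might infer that the two doses will be compared only by eye and that the uncertainty will be hidden. The documents do not support that: geometric means, CVs and numbers by dose are committed, and anyone could derive the ratio and its interval from them. A reader might also infer that the primary objective is compromised or that a false claim of proportionality will be made. Neither follows, because the objective is to characterise PK and the protocol plans no such claim.

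A further objection is that an interval could lend the comparison too much authority. Cohort 2 opens only after Cohort 1 has filled, without randomisation, so dose is confounded with enrolment period and case mix. That is right and calls for a caveat. It affects the plots equally, so it is no reason to prefer reading them by eye.

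What the reply does not remove is that, where the protocol raises the question, the only tool it names yields no estimate, although a better one is available from the same data.

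**Conclusion.** The point holds as a minor one. The named method for proportionality is optional visual inspection. No ratio or interval between doses is planned for any parameter, and nothing dose-normalised is planned for Cmax or the metabolites. At assumed CVs of 30% to 60% and 12 evaluable per cohort, the 90% CI would be the estimate times or divided by 1.23 to 1.48, and wider with fewer patients. An apparently proportional plot would therefore still be compatible with departures of roughly a fifth to a half.

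The size rests on the assumed CVs, a common log-scale SD in the two cohorts, and the evaluable number. The study can offer an estimate of proportionality, not a demonstration of it. This calls for neither a larger sample nor a formal test.

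**What to change.** Keep the plots. In section 7.7 and the synopsis add, for each of AZD9291, AZ5104 and AZ7550, the 80/40 ratio of dose-normalised geometric means with a 90% CI from a two-sample model on the log scale:
- after the single dose: AUC, AUC(0-24) and Cmax;
- at steady state: AUCss and Css,max.

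Label the results descriptive, set no acceptance limit, and show the actual number evaluable for each parameter. State beside the table that the cohorts were enrolled one after the other without randomisation, so the interval covers between-patient variation only and not differences in enrolment period or case mix.

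The cost is one extra table from data already collected. No samples, visits or patients are added.

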8. IMPORTANT MEDICAL PROCEDURES TO BE FOLLOWED BY THE INVESTIGATOR

8.1 Medical emergencies and AstraZeneca contacts

The Principal Investigator(s) is responsible for ensuring that procedures and expertise are available to handle medical emergencies during the study. A medical emergency usually constitutes an SAE and is to be reported as such, see Section 6.4.4.

In the case of a medical emergency the investigator may contact the Study Team.

8.2 Overdose

There are no data on overdosing since this is the first study in humans with AZD9291. There is no definition of what constitutes an overdose. There is no known antidote. Investigators will be advised that any patient who receives a higher dose than that intended should be monitored closely, managed with appropriate supportive care and followed up expectantly.

Such overdoses should be recorded as follows:

- An overdose with associated AEs/SAEs is recorded as the AE diagnosis/symptoms on the relevant AE/SAE modules in the eCRF and on the overdose eCRF module.
- An overdose with no associated symptoms is only reported on the overdose eCRF module.

If an overdose occurs in the course of the study, then investigators or other site personnel inform appropriate AstraZeneca representatives immediately, or **no later than 24 hours** of when he or she becomes aware of it.

The designated AstraZeneca representative works with the investigator to ensure that all relevant information is provided to the AstraZeneca Patient Safety data entry site.

For overdoses associated with an SAE, standard reporting timelines apply, see Section 6.4.4. For other overdoses, reporting should be done within 28 days.

8.3 Pregnancy

All pregnancies and their subsequent outcome (spontaneous miscarriage, elective termination, ectopic pregnancy, normal birth or congenital abnormality) should be reported to AstraZeneca using the appropriate forms.

8.3.1 Maternal exposure

If a patient becomes pregnant during the course of the study investigational product should be discontinued immediately.

Pregnancy itself is not regarded as an adverse event unless there is a suspicion that the investigational product under study may have interfered with the effectiveness of a contraceptive medication. Congenital abnormalities/birth defects and spontaneous miscarriages should be reported and handled as SAEs. Elective abortions without complications should not be handled as AEs. The outcome of a pregnancy should be followed up and documented even if the patient was withdrawn from the study.

If a pregnancy occurs during exposure to investigational product or in the 28 days after discontinuing investigational product, then investigators or other site personnel inform appropriate AstraZeneca representatives immediately, or **no later than 24 hours** of when he or she becomes aware of it.

The designated AstraZeneca representative works with the investigator to ensure that all relevant information is provided to the AstraZeneca Patient Safety data entry site within 1 or 5 days for SAEs, (see Section 6.4.4) and within 28 days for all other pregnancies.

The same timelines apply when outcome information is available.

